9.0 Criteria for Removal from the Study

1. Any patient can be removed from study if, in the judgment of the Principal Investigator, further treatment is not in the best interest of the patient for whatever reason.
2. Disease progression after DLI.
3. Death.
4. Patient withdraws informed consent.
5. First bone marrow aspiration performed after transplantation showing primary engraftment failure.
6. Inability or unwillingness to have follow-up visits and/or laboratory tests required by this protocol.

10.0 Data and Protocol Management

Data necessary to assess and analyze primary and secondary objectives of this study will be collected in the departmental research database at different time points as mandated by the study plan.

Adverse event (toxicity) definition and data collection:

An AE is defined as any untoward medical event, including worsening of increased frequency of an event present at baseline, in a subject registered in this study and receiving Fludarabine/Busulfan//ATG plus allogeneic stem cell transplant or unanticipated benefit, without regard to the possibility of a causal relationship.

In this study, patients are expected to experience changes in laboratory parameters due to the underlying disease and the nature of the treatment for allogeneic stem cell transplant. These expected changes will not be considered AE(s) and will not be recorded in the database unless in the view of the investigator they are judged to be clinically significant.

Transplant related adverse events:

For the purpose of this study, common transplant related AE are those known to be related to the preparative regimen and stem cell infusion occurring up to 30 days post transplant. The most common are listed below.

Neutropenic Fever without infection, non-Neutropenic fever, infections associated with grade 3 or 4 neutropenia, nausea and vomiting, readmission during the active treatment period (D+30 post stem cell infusion) transfusions of platelets and RBCs,

low blood pressure due to dehydration requiring fluid replacement, mucositis, engraftment syndrome. These events will be monitored and captured in the database during the first 30 days post transplant.

The following common transplant related events will be captured in the database any time when observed: cytopenias post-transplant, including secondary graft failure whether or not leading to death, hemorrhagic cystitis, liver function test abnormalities associated with VOD, TTP, significant infections and graft vs. host disease.

AE Assessment

AE(s) will be assessed according to the revised NCI Common Terminology Criteria for Adverse Events (CTCAE) version 3.0

Reporting Adverse Events:

Serious and unexpected adverse events will be reported accordingly to MDACC guidelines and the BMT reporting requirements. The end of active treatment is the day of the allogeneic stem cell infusion. These events will be reported to the study chairman, who in turn will notify the MDACC IRB.

11.0 Background Drug Information

11.1 Busulfan Injection

Therapeutic Classification: Antineoplastic Alkylating agent

Pharmaceutical data: Busulfan injection is a sterile, pyrogen-free solution provided in a mixture of dimethylacetamide (DMA) and polyethyleneglycol 400 (PEG400). It is supplied in 10 ml single use ampoules at a concentration of six (6) mg busulfan per ml. Each ampoule contains 60 mg of busulfan in 3.3 ml of DMA and 6.7 ml of PEG400. When diluted in normal saline or D5W to a concentration of 0.5 mg/ml, the resulting solution must be administered within eight (8) hours of preparation including the three (3) hour infusion of the drug.

Stability and storage: Ampoules should be stored refrigerated at 2-8°C (35-46°F). Stable at 4°C for at least twelve (12) months. Additional stability studies are in progress. DO NOT use beyond the expiration date. DO NOT use if the solution is cloudy or if particulates are present.

Solution Preparation: Prepare the busulfan solution as follows (The patient is to receive a dose of 130 mg/m² of busulfan):

Use sterile, non-pyrogenic, disposable containers, syringes, needles, filters, stopcocks, and transfer tubing, etc.

All transfer procedures require strict adherence to aseptic techniques. Preferably, these transfer procedures will be carried out in a laminar flow hood.

Calculate the amount of drug to be administered based on the dosage of 130 mg/m² and the patient's body surface. For example: A 70 kg patient with a height of 170 cm, (BSA of 1.8 m²) who receives a dose of 130 mg/m² of busulfan (6mg/ml) would receive 39 ml of busulfan for injection:

$$(1.8 \text{ m}^2)(130 \text{ mg /m}^2) \cdot (6\text{mg/ml}) = 39 \text{ ml busulfan.}$$

Prepare a solution of 0.9% Sodium Chloride Injection USP (normal saline), that is 10 times the volume of the calculated busulfan dose in ml from the step above (39 ml busulfan). This preparation will insure a final concentration of at least 0.5 mg busulfan/ml. For example, (39 mL dose) x (10) = 390 mL of normal saline. The final volume of solution will be 390 + 39 = 429 mL

$$(390 \text{ mL} + 39 \text{ mL} = 429 \text{ mL})$$

The resulting busulfan concentration will be 0.545mg/ml
(234 mg ÷ 429 mL = 0.545 mg/mL).

In each bag 6.0 mg busulfan (1.0 ml at 6 mg/ml and 11 ml saline) should be added to compensate for drug lost in the tubing with each infusion (approximately 12 ml at 0.5 mg/ml is lost in the tubing).

Break off the top of the ampoule and use a syringe needle to remove the calculated volume of busulfan from the primary container. Remove the needle, replace with a new needle which has been fitted with a 5.0 micron nylon filter (provided with packaged drug) and transfer the contents of the syringe into the calculated amount of either normal saline or D5W making sure that the drug flows into and through the solution. Do not put the busulfan solution into a syringe or IV bag, which does not contain the normal saline or D5W. Mix by inverting the container numerous times to ensure a homogenous solution. Place an appropriate label on the container with an expiration time of eight (8) hours from the time of preparation with directions to store at room temperature. Do not use if solution contains visible particulates. Record the actual volume on the label (429 mL in the example).

Place a suitable (non-vented or universal) intravenous administration set (gravity flow) into the outflow port of the container of the infusion solution.

Route of Administration: It is to be noted, that a sufficient amount of diluted busulfan should be added to compensate for the amount needed to prime the IV tubing; when hanging the infusate, the tubing should be primed with the busulfan solution and connected as close to the patient as possible, i.e. by a 3-way connector at the level of the central venous catheter. After completed infusion, the tubing with remaining busulfan (approximately 12 mL) should be disconnected and discarded. All busulfan

infusions should be performed by programmable pump.

The busulfan will be given by slow intravenous infusion over three (3) hours into a central venous catheter.

CAUTION: DO NOT ADMINISTER AS AN INTRAVENOUS PUSH OR BOLUS.

An infusion pump will be used with the busulfan solutions as prepared above. A new infusion set must be used for administration of each dose. Prior to and following each infusion, flush the catheter line with normal saline or (approximately 5 ml). Start the three-hour infusion at the calculated flow rate (i.e. 429 mL/180 min 2.4 mL/min). DO NOT infuse concomitantly with another intravenous solution of unknown compatibility.

If a delay in administration occurs after the infusion solution is prepared, the properly identified container should be kept at room temperature (20-25°C), but administration must be completed within eight (8) hours of preparation including the three (3) hour drug infusion.

Known Side effects: Dose limiting toxicity is expected to be hematological when used without stem cell support. Other toxicities seen frequently following high-dose busulfan in preparative regimens for bone marrow transplantation include: VOD, nausea, vomiting, pulmonary fibrosis, seizures, rash, and an Addison's-like syndrome.

Mechanism of action: Interferes with DNA replication and transcription of RNA through DNA alkylation, and ultimately results in the disruption of nucleic acid function.

Animal Tumor Data: Busulfan has been shown to be active against a variety of animal neoplasm in vivo, including mouse sarcoma 180 and Ehrlich's mouse ascites tumor.

Animal Toxicology: Busulfan fed to rats in an amount equivalent to about 0.5 mg/kg of final body weight per day slowed weight gain and produced bone marrow depression, pancytopenia and cataracts after about 10 weeks. In rats, LD50 was found to be 34 mg/kg intraperitoneally. When the drug was administered on day 13, 14, or 15 of gestation at a dose of 10 mg/kg to rats, the progeny were prematurely sterile.

Human Pharmacology: Limited pharmacology data are available for the parenteral formulation to be used in this study and is detailed in Attachment II, Preliminary Pharmacokinetic Evaluation of Busulfan in a Phase II human Trial. The pharmacokinetic data suggests that the plasma decay of the formulation fits a two-compartment model. The oral formulation is absorbed from the gastrointestinal tract, and measurable blood levels are obtained within one-half to two (0.5-2.0) hours after ingestion. Within three (3) minutes after IV administration in rats, 90% of the drug disappears from the blood; similar rapid decreases in blood concentrations have been reported in man. Busulfan is reported to be extensively metabolized; twelve (12) metabolites have been isolated, but most have not been identified. The drug is slowly excreted in the urine, chiefly as methanesulfonic acid. Ten to fifty percent (10-50%) of

a dose is excreted as metabolites within twenty-four (24) hours.

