5.0 Treatment Plan

5.1 Preparative Regimen

Treatment will start on D-7 as per the schema shown below:

-7	-6	-5	-4	-3	-2	-1	0
		Flu	Flu	Flu	Flu		
Bu test dose 32 mg/m ²	Rest	Bu	Bu	Bu	Bu		
				ATG*	ATG*	ATG*	
							HSCT

Fludarabine 40mg/m²/day IV over 60 mins x 4 days (days -5,-4,-3, and -2)

Busulfan (days -5,-4,-3, and -2)

Rabbit ATG (Thymoglobulin) 2.5 mg/kg (infused over 6 hours) X 3 days (day -3,-2 and -1)*

*Patients with HLA-identical sibling donors do not receive Thymoglobulin.

Donor bone marrow or blood stem cells to be infused on day 0.

BUSULFAN is administered at the dose of 100 mg/m² in normal saline over three (3) hours i.v. every twenty-four (24) hours for four (4) consecutive days (days -5 to -2). The busulfan dose on day -5 to -2 will be altered on the basis of the pharmacokinetic studies to target an AUC of 4000 mMol-min ± 12%. This altered dose will be administered in an identical fashion to the 100 mg/m² dose. If the patients cannot undergo the pharmacokinetic studies, the patient will not receive the 32 mg busulfan "test dose" and will receive the 100 mg/m² dose day -5 to -2. Patients may also undergo the busulfan test dose as an outpatient, with inpatient admission on day -6.

Busulfan pharmacokinetic studies: Patients will receive a test dose of busulfan at 32mg/m² i.v. over on day – 7 for measurement of pharmacokinetics to determine the dose that will give a daily AUC of 4000 μ Mol-min \pm 12% on days –5 through day –2. Blood samples (5ml each) will be drawn on day –7 at 30 min after the start of infusion and 5 min. before the end of infusion, then after the end of infusion at 15, 30, 60 min. and at 2, 4, 6 and 8 hours, and one sample approximately 10-11 hours.

Pharmacokinetic analysis and individualized IV busulfan dose will be calculated and ordered on day –6. Follow-up PK samples (quality control) will be drawn on days –5 and if necessary, for fine-tuning of the busulfan dose, and if necessary on day –3. Patients receiving the fixed-dose treatment arm will also have PK studies performed on day(s) –5, and if necessary on day –3 to allow for monitoring and if necessary, adjustment of busulfan dosing per above. This complete sampling schedule will be replaced with a limited sampling schedule when a validated limited sampling assay becomes available.

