8.0 Statistical Considerations

This is a phase II study with a primary objective of assessing the safety of Fludarabine, and Busulfan as preparative regimens for allogeneic stem cell transplantation in patients with Myelofibrosis and MDS. Patients enrolled in the study will be younger than 75 years of age and must have an HLA matched or at least a 9/10 antigen matched related or unrelated donor. The major reason for treatment failure in these patients is transplant related mortality. Therefore, in order to assess the primary objective of safety, the primary outcome measure will be the rate of non-relapse mortality (NRM) at 100 days. We will define non-relapse mortality as any death not attributable to disease recurrence. The cumulative incidence rates of NRM ranged from 27%-48% in three studies of younger patients with this disease. The NRM rate is expected to be much higher in this mostly older group of patients with advance myelofibrosis we are proposing to treat because NRM increases with age and coexisting medical illnesses. Therefore, the goal of the trial is to achieve better than a 30% NRM rate at 100 days post transplant with this treatment regimen. The proposed trial will evaluate the role of allogeneic stem cell transplantation a using reduced-intensity conditioning regimen of fludarabine and busulfan. These patients will receive 4 days of the Fludarabine regimen and 2 days of the Busulfan regimen. The maximum total sample size for this trial was originally 30 patients. It was increased in July 2009 to 60 patients. As of September 2011, 49 patients have been enrolled, and we now plan to increase enrollment to 110 patients. We expect to accrue 20 patients a year for a total of 3 years. The goal of the trial is to achieve better than a 30% NRM rate at 100 days post transplant. We will stop the trial if we have evidence that the NRM rate is higher than targeted.

The method of Thall and Simon will be employed to perform interim safety monitoring. As of September 2011, a total of 49 patients have been enrolled, of which 45 have been evaluated for NRM at day 100. Monitoring has proceeded according to the original stopping rule with no need for early study termination. For the remaining 65 patients, we will employ the following monitoring rule. The trial will be stopped early if:

$$\Pr[\theta \in E, D > 0.30 | \text{data}] > 0.90$$

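### Section 11.1 tells staff to prepare busulfan at 130 mg/m², but the treatment plan in Section 5.1 orders 100 mg/m² or a PK-directed dose

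*Combined protocol and SAP*

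**What the plan says.** **Treatment plan.** Section 5.1 states: "BUSULFAN is administered at the dose of 100 mg/m²", given over three hours once daily on days -5 to -2. The dose is then altered to reach a daily AUC of 4000 µMol-min ± 12%. There are two routes:

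- Patients with a 32 mg/m² test dose on day -7 have their own dose set before treatment starts: the "individualized IV busulfan dose will be calculated and ordered on day" -6.
- Patients who cannot have these PK studies skip the test dose and "will receive the 100 mg/m² dose day -5 to -2". They have PK sampling on day -5 and, if necessary, day -3, with adjustment allowed.

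**Preparation instructions.** Section 11.1 states: "The patient is to receive a dose of 130 mg/m² of busulfan". It then directs: "Calculate the amount of drug to be administered based on the dosage of 130 mg/m²" and the patient's body surface. Its worked example for a 1.8 m² patient arrives at 39 mL of drug and a 429 mL bag. The administration text carries the example on: "Start the three-hour infusion at the calculated flow rate (i.e. 429 mL/180 min 2.4 mL/min". Section 11.1 mentions neither 100 mg/m², nor the test dose, nor a PK-directed dose.

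**Statistical section.** Section 8.0 gives a different duration: "These patients will receive 4 days of the Fludarabine regimen and 2 days of the Busulfan regimen". The schema and text of Section 5.1 consistently give four days of each drug.

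**The concern.** Two sections give different doses of the same cytotoxic drug, and the higher figure is in the text addressed to the person preparing it. The protocol has no clause saying which section prevails. The choice of dose is not in question; the problem is that the document contradicts itself.

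The study uses reduced-intensity conditioning, and its primary objective is safety, measured by non-relapse mortality. Section 11.1 itself lists VOD, seizures and pulmonary fibrosis among the frequent toxicities of high-dose busulfan. By September 2011, 49 of the planned 110 patients had enrolled, so 110 - 49 = 61 were still to be treated under this text.

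A patient on the fixed-dose route receives the day -5 dose before any PK result exists. If that dose were prepared from Section 11.1, the PK sampling could detect the excess only after it had been given.

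**Working it through.** **Inputs.** The planned nominal dose of 100 mg/m² on four days, and the AUC target of 4000 ± 12%, are from Section 5.1. The preparation dose of 130 mg/m², body surface of 1.8 m², ampoule strength of 6 mg/mL, saline at 10 times the drug volume and infusion time of 180 minutes are from Section 11.1.

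**Formulas.** Dose = body surface × mg/m². Drug volume = dose / 6. Final volume = drug volume × 11. Concentration = dose / final volume. Flow rate = final volume / 180.

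**Step 1: reproduce the protocol's example, then repeat it at the planned dose.**

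| | 130 mg/m² (Section 11.1) | 100 mg/m² (Section 5.1) |
|---|---|---|
| Dose | 1.8 × 130 = 234 mg | 1.8 × 100 = 180 mg |
| Drug volume | 234 / 6 = 39 mL | 180 / 6 = 30 mL |
| Saline | 390 mL | 300 mL |
| Final volume | 429 mL | 330 mL |
| Concentration | 234 / 429 = 0.545 mg/mL | 180 / 330 = 0.545 mg/mL |
| Flow rate | 429 / 180 = 2.38 mL/min | 330 / 180 = 1.83 mL/min |

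The first column matches every figure printed in Section 11.1, so its arithmetic is sound and only its starting dose conflicts. The excess is 234 / 180 = 1.30, or +30%: 54 mg and 9 mL per dose. The concentration is the same in both columns, so checking concentration would not show the difference. The tubing allowance is 6 mg per bag at either dose and does not explain the gap.

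**Step 2: effect on the course.** The plan without PK adjustment is 4 × 100 = 400 mg/m².

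- First dose at 130: 130 + 3 × 100 = 430 mg/m² (+7.5%).
- First two doses at 130: 2 × 130 + 2 × 100 = 460 mg/m² (+15%).

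**Step 3: comparison with the protocol's exposure target.** The band is 4000 × 0.88 = 3520 to 4000 × 1.12 = 4480. The documents give no relation between dose and AUC, so proportionality is assumed here. A patient inside the band at 100 mg/m² would reach 3520 × 1.3 = 4576 to 4480 × 1.3 = 5824 at 130 mg/m², wholly above the upper limit. Conversely, 130 mg/m² lands inside the band only if AUC at 100 mg/m² lies between 3520 / 1.3 = 2708 and 4480 / 1.3 = 3446, that is, in a patient below target at the planned dose.

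**Step 4: who is exposed.** On the PK-guided route the individual dose is ordered a day before the first therapeutic infusion. On the fixed-dose route the day -5 dose precedes any PK result; the day -4 dose may do so too, depending on assay turnaround, which the documents do not state.

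**The case against.** The strongest reply is that a careful reader would follow Section 5.1. It is the treatment plan and gives 100 mg/m² repeatedly, while Section 11.0 is headed as background drug information. On the default PK-guided route Section 11.1 cannot be followed literally, since neither the test dose nor the individualized dose is set at 130 mg/m². A preparer must already substitute the ordered dose, which makes 130 look like a leftover figure. The 39 mL, 429 mL and 2.4 mL/min figures are illustrations, to be recalculated for each patient. The volume must be written on the label, and 429 mL is visibly different from 330 mL. The size of the fixed-dose group is not given, and adjustment after day -5 is allowed. The AUC argument is conditional, because a fixed-dose patient's AUC at 100 mg/m² is unknown beforehand. Of 45 evaluated patients, 43 had no non-relapse mortality.

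Much of this stands as a limit on exposure: a pharmacy would normally prepare what was ordered, and the risk is narrow. It does not remove the contradiction. The 130 mg/m² figure is stated as the dose the patient receives, and as the basis for calculation, before the example begins. These are also the protocol's only busulfan preparation instructions. The background heading does not change wording that reads as an instruction, and the label volume reveals an error only to someone who knows the correct volume. The favorable early mortality count is no signal of harm, but it does not show which dose was prepared.

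**Conclusion.** The concern holds. Section 11.1 gives a preparation dose 30% above the nominal dose in Section 5.1. This is a wrong operative dose figure with a possible consequence for patients, and it should be corrected.

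The realistic exposure is the day -5 dose, and possibly day -4, in patients without test-dose PK. The statement that exposure would exceed the AUC limit rests on dose-proportional AUC and on a patient who would be within target at 100 mg/m². It is also assumed that Section 5.1 is the intended plan, which the investigator should confirm.

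The definition of non-relapse mortality, the stopping boundaries and the operating characteristics do not depend on dose and are unaffected. The two-day busulfan statement in Section 8.0 is a separate editorial error.

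**What to change.** After the investigator confirms that Section 5.1 governs:

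1. In Section 11.1, replace both 130 mg/m² instructions with a reference to the dose ordered under Section 5.1. That wording covers the test dose, the fixed 100 mg/m² dose, the PK-directed dose and any later adjustment.
2. Rework the example at 100 mg/m²: 180 mg, 30 mL busulfan plus 300 mL saline, 330 mL final volume, about 1.83 mL/min, before the 12 mL tubing allowance. Change the example label volume and pump rate to match.
3. In Section 8.0, give four days of busulfan.

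An optional addition is to record the milligrams actually given at each dose. If a 130 mg/m² dose were logged as 100, the PK correction would itself mislead. With a true AUC of 4000 at 100 mg/m² and proportional exposure, the measured 5200 would prompt a cut to 100 × 4000 / 5200 = 77 mg/m², giving an AUC of about 3077, below the 3520 limit.

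The cost is a text amendment to Section 11.1 and one sentence of Section 8.0, with no change to design, sample size or monitoring.

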11.2 Fludarabine

Therapeutic Classification: fluorinated nucleoside analog

Pharmaceutical Data: Each vial contains 50 mg lyophilized drug, to be reconstituted with 2 ml sterile water to a solution that is 25 mg/ml for IV administration.

Solution Preparation: mix each vial with 2 ml sterile pyrogen-free water to a clear solution, which is 25 mg/ml for IV administration only. Reconstituted solution should be used within 8 hours.

Known Side Effects: pancytopenia, immunosuppression, autoimmune hemolytic anemia has (rarely) been reported, and recurred when patients were retreated with the drug. Nausea, vomiting, anorexia, weakness. From the CNS: agitation, visual disturbances, confusion, coma, peripheral neuropathies have been reported. With high dose use confusion, blindness, coma and death have been reported.

Special Precautions: As for other antineoplastic agents Fludarabine should be handled by trained personnel using procedures for proper handling. The use of gloves and protective glasses is recommended to avoid exposure upon accidental spillage.

Mechanism of Action: After phosphorylation to fluoro-ara-ATP the drug appears to incorporate into DNA and inhibit DNA polymerase alpha, ribonucleotide reductase and DNA primase, thus inhibiting DNA synthesis.

Human Safety and Pharmacology: The half-life of the activated compound is approximately 10 hours, but the pharmacology is incompletely understood. Excretion is impaired in patients with impaired renal function.

